Hypothesis 2A: We will be able to identify baseline characteristics (demographics and baseline severity measures, as well as QEEG abnormalities) that influence change in the primary outcome measure (change in CU in picture description from baseline to 1-week post-treatment).

Hypothesis 2B. We will be able to identify changes in secondary outcome measures and changes in qEEG that correlate with the primary outcome measure (change in CU from baseline to post-treatment). These results will allow us to identify variables to explore as interaction variables.

Tertiary Objective: To determine if EEG neurofeedback training is associated with improved physiological measures of neural connectivity via qEEG assessment and fNIRS. This Aim is also exploratory, as we do not have any preliminary data on which to base hypotheses about the effects of EEG neurofeedback on physiological measures of neural connectivity.

Hypothesis 3A: Greater improvement in qEEG normalization (e.g. alpha enhancement) will be observed in the EEG neurofeedback training condition compared to sham training condition.

Hypothesis 3B. Greater connectivity within the attentional network and the language network (and right hemisphere homologues) will be observed in the EEG neurofeedback training condition compared to sham training condition.

3. **Background** (briefly describe pre-clinical and clinical data, current experience with procedures, drug or device, and any other relevant information to justify the research)

Date: November 11, 2021
Principal Investigator: [name]
Application Number: IRB00242136
NCT# NCT04290988
Study Title: Circuitry Assessment and Reinforcement Training Effects on Recovery (CARTER)

There is a need for improved behavioral interventions and objective instrumentation for behavioral syndromes following stroke and in neurodegenerative disease. Sophisticated techniques are needed to provide specific reinforcement to capitalize on principles of neuroplasticity and brain rehabilitation. Z-score neurofeedback training could fill this gap. Neurofeedback training allows conditioning and change to occur on a behavioral level. It is hypothesized that these behavioral changes may correlate with physiological changes that can be identified on qEEG recording and fNIRS.

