In the past few decades, analysis of EEG recording has become more sophisticated, with the discovery of "source analysis." EEG signals can instantaneously perceive electrical current variations in the brain. Real-time EEG applications such as neurofeedback and brain-computer interfaces that capitalize on the high-temporal resolution of EEG have become an area of interest for potential clinical applications. The most direct method for using qEEG information to guide

Date: November 11, 2021
Principal Investigator: [name]
Application Number: IRB00242136
NCT# NCT04290988
Study Title: Circuitry Assessment and Reinforcement Training Effects on Recovery (CARTER)

neurofeedback training utilizes training protocols based on z-score deviation for a specific feature. This is called live z-score training (Johnstone & Lunt, 2011).

This study aims to investigate what behavioral and physiological changes can occur in individuals with communication impairments when we reinforce healthier circuitry by reinforcing improved synchronous firing patterns (e.g. enhanced alpha) through EEG biofeedback. There is accumulating literature suggesting that there is value in using EEG information for guiding clinical intervention with medication and neurofeedback (Johnstone & Lunt, 2011).

Since neurofeedback is a learning technique, it has potential for intrinsically lasting effects. Collura (2014) proposed that these “brain exercises” have potential to implement changes that produce the desired feedback and increase self-regulation. Collura hypothesized possible mechanisms of EEG neurofeedback training to include changes in cortical excitability, generation and uptake of neurotransmitters, and cortical and subcortical connectivity. Trainees may benefit from physiological and behavioral changes. Physiological changes may be validated by repeated qEEG assessment, and behavioral changes can be measured through neuropsychological testing.

Since behavioral training is based on principles of neuroplasticity, operant conditioning, and learning principles, it is possible that this type of network-level skill learning could increase recruitment of novel pathways in PPA and in stroke recovery and strengthen current neural network pathways. This modality could also maximize brain regulation to support efficient brain activity for creation of novel pathways during neurorehabilitation. Results of this study could inform future work in behavioral interventions in neurorehabilitation.

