It is commonly believed that aphasia recovery involves major reorganization of structure/function relationships, including shifts of language to the right hemisphere following left hemispheric stroke. Changes over time in the intrinsic connectivity networks in the brain, studied with resting state (“task free”) fMRI and fNIRS are likely to reveal additional insights regarding aphasia and cognitive recovery. Whether or not normalizing brainwave patterns via EEG neurofeedback training supports and/or enhances increased functional connectivity in the brain is currently not known. To investigate the effects of more normalized brainwave patterns on functional connectivity, we will also collect task-based and task-free (“resting”) functional Near-Infrared Spectroscopy (fNIRS) data at the baseline, 1-week post-treatment, and 5-week post-treatment follow-up assessment time points. The fNIRS protocol is expected to take up to 60 minutes and will be completed in the same location in which we administer behavioral assessments. fNIRS is a safe, non-invasive, and flexible modality for brain imaging. It capitalizes on the fact that near-infrared light can propagate several centimeters through tissue because of low optical absorption by hemoglobin and water at specific wavelengths. During an fNIRS experiment, an array of light sources and detectors affixed to a cap is placed on the scalp, and the measures from these different channels allow the reconstruction of an image of the hemodynamic response. fNIRS has emerged as a complementary technology to other brain

Date: November 11, 2021
Principal Investigator: [name]
Application Number: IRB00242136
NCT# NCT04290988
Study Title: Circuitry Assessment and Reinforcement Training Effects on Recovery (CARTER)

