To test this hypothesis, we will carry out Pearson correlations between the dependent variable (change in CU in picture description from baseline to 1-week post-treatment), and change in CU, change in OANB, change in COWA, change in absolute power and peak amplitude frequency within each frequency band (alpha, beta, theta, delta, gamma) on qEEG, change in coherence on qEEG (e.g., coherence between left and right hemispheres).

Hypothesis 3A is: Greater improvement in qEEG normalization toward healthy control group (e.g. alpha enhancement with absolute power and peak amplitude frequency ≤ 1.5 standard deviations away from healthy group average) will be observed in the EEG neurofeedback training condition compared to sham training condition.

Date: November 11, 2021
Principal Investigator: [name]
Application Number: IRB00242136
NCT# NCT04290988
Study Title: Circuitry Assessment and Reinforcement Training Effects on Recovery (CARTER)

To test this hypothesis, we will compare baseline and follow-up z-scores for absolute power and peak amplitude frequency of each of the frequency bands (alpha, beta, theta, delta, gamma) by subtracting the absolute value baseline z-score from the absolute value follow-up z-scores for each condition. We will use paired t-tests to determine if, as a group, patients showed greater improvement during the neurofeedback condition compared to the sham condition, at each follow-up. We will correct for multiple comparisons using a Bonferroni correction. We will also carry out paired t-tests for post-stroke aphasia and PPA separately, to determine if the effect was greater in one group.

Hypothesis 3B is: Greater connectivity within the attentional network and the language network (and right hemisphere homologues) will be observed in the EEG neurofeedback training condition compared to sham training condition.

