To test this hypothesis, we will compare baseline and follow-up z-scores for coherence in each of the frequency bands (alpha, beta, theta, delta, gamma) by subtracting the absolute value baseline z-score from the absolute value follow-up z-scores for coherence in each condition. We will use paired t-tests to determine if, as a group, patients showed greater improvement during the neurofeedback condition compared to the sham condition, at each follow-up. We will correct for multiple comparisons using a Bonferroni correction. We will also carry out paired t-tests for post-stroke aphasia and PPA separately, to determine if the effect was greater in one group.

c. Statistical plan including sample size justification and interim data analysis

Statistical Analyses

Statistical tests to evaluate each hypothesis are described above. No interim data analyses are planned, although we will become unmasked to condition after each participant completes the 5 week follow-up

Sample Size Determination

This study is a novel application of neurofeedback for treatment of aphasia, and we have no preliminary data to guide a power analysis. However, we will use this preliminary cross-over study (with each patient as their own control) to identify effect size (if any), in order to plan a randomized, double-blind, parallel, sham-controlled trial. For this preliminary trial, we plan to study 8 patients per year with post-stroke aphasia, and 8 patients per year with PPA, based on our other ongoing trials of post-stroke aphasia and PPA, in which we have found that it is feasible to recruit and retain 8-10 of each per year. We hope to obtain a total of 40 patients with post-stroke aphasia and 40 with PPA over 5 years, to obtain preliminary data for a multicenter, randomized, double-blind, parallel, sham-controlled trial, if the preliminary results are positive.

Missing Data

We plan to minimize missing data by avoiding prolonged intervals between conditions. Most of the study will take place within 7-11 weeks, with each person scheduled to have a 5 week follow up to determine if any changes are long-lasting. To minimize biases, analyses will be by

Date: November 11, 2021
Principal Investigator: [name]
Application Number: IRB00242136
NCT# NCT04290988
Study Title: Circuitry Assessment and Reinforcement Training Effects on Recovery (CARTER)

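### Hypothesis 3B predicts greater connectivity, but its test scores distance of coherence from the norm, so a fall in coherence can count as success and a rise as nothing or a worsening

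*Combined protocol and SAP*

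**What the plan says.** The hypothesis is directional. Section 2 (Tertiary Objective) and Section 7b both state it as "Greater connectivity within the attentional network and the language network (and right hemisphere homologues) will be observed in the EEG neurofeedback training condition", compared with sham. Neither statement mentions normalisation.

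The measure is the qEEG coherence z-score in each of five frequency bands. The introductory section explains that qEEG compares the patient with a normative database. The change score is formed "by subtracting the absolute value baseline z-score from the absolute value follow-up z-scores for coherence in each condition". Active and sham changes are then compared by paired t-test for greater improvement, with a Bonferroni correction. Section 7b does not say whether a lower or a higher value is improvement.

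The same formula is used just above for Hypothesis 3A, which is about something else: "Greater improvement in qEEG normalization toward healthy control group".

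**The concern.** A z-score against a normative database has a sign: negative means less coherence than healthy peers, positive means more. Taking absolute values discards that sign. What remains suits 3A, which asks whether patients move closer to the norm. It does not suit 3B, which asks whether connectivity goes up.

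Two wrong conclusions become possible. If training pulls deviant values toward the norm from both sides, the 3B test can support greater connectivity when mean coherence has not changed or has fallen. If training raises coherence in patients near or above the norm, the test can show nothing, or a worsening.

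Section 7c says the trial is meant to identify effect sizes for a later trial. An effect on normalisation reported as an effect on connectivity would carry the wrong label into that planning.

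**Working it through.** The plan gives no effect size, SD or power for 3B, so there is no figure of its own to reproduce. The mismatch follows from the formula; the simulation only shows how large it could be.

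**Step 1: the formula on single patients.** Planned score = abs(z at follow-up) - abs(z at baseline). Signed change = z at follow-up - z at baseline. The last column takes a lower absolute z as improvement, the reading implied by 3A and by the Background's description of "training protocols based on z-score deviation for a specific feature".

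| Baseline z | Follow-up z | Signed change | Planned score | Counted as |
|---|---|---|---|---|
| -2 | -1 | +1 | 1 - 2 = -1 | improvement (correct) |
| +2 | +1 | -1 | 1 - 2 = -1 | improvement (coherence fell) |
| -0.5 | +0.5 | +1 | 0.5 - 0.5 = 0 | no change (coherence rose) |
| +0.5 | +2 | +1.5 | 2 - 0.5 = +1.5 | worsening (coherence rose) |

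Reversing the convention does not help: a fall from -0.5 to -2 scores 2 - 0.5 = +1.5 and would then count as success. Neither convention tests an increase.

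**Step 2: group means.** For z normal with mean m and SD 1, the mean of abs(z) is sqrt(2/pi) x exp(-m²/2) + m x (1 - 2 x Phi(-m)). This gives 2.017 at m = -2, 1.559 at -1.5, 1.167 at -1, 0.896 at -0.5 and 0.798 at 0, with the same values at +m. If every patient's coherence rises by 0.5, the mean planned score is:

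- baseline -2: 1.559 - 2.017 = -0.458
- baseline -1: 0.896 - 1.167 = -0.271
- baseline -0.5: 0.798 - 0.896 = -0.098
- baseline -0.25: 0 (the mean moves to +0.25, the same distance from the norm)
- baseline 0: +0.098
- baseline +0.5: +0.271

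The same true rise changes sign in the planned score at minus half the gain.

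**Step 3: illustration of test results.** From the documents: 80 patients (40 + 40, the hoped-for total in Section 7c), five bands, and three assessments (Visit 18 is both the Phase I follow-up and the Phase II baseline). Assumed: z SD 1; between-visit correlation 0.8; two-sided alpha 0.05/5 = 0.01; half the patients in each sequence; 10,000 simulated trials per cell. Each pair of figures is: effect persists after the active period / does not persist.

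*Normalisation: each patient's true z moves 50% of the way to 0.*

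| Baseline mean | Mean coherence | Planned test: improvement | Signed test |
|---|---|---|---|
| -1 | rises 0.5 | 97% / >99% | rise in 87% / 99% |
| 0 | unchanged | 58% / 91% | rise in about 0.5% |
| +1 | falls 0.5 | 97% / >99% | fall in 87% / 99% |

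The -1 row is the mirror image of the +1 row. With 30% movement at baseline 0, the planned test shows improvement in 20% / 47%.

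*Uniform true rise of 0.5.* The signed test detects it in 92% / >99% at every baseline. The planned test gives:

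| Baseline mean | Planned test |
|---|---|
| -2 | improvement 88% / >99% |
| -1.5 | improvement 76% / 98% |
| -1 | improvement 39% / 75% |
| -0.5 | improvement 4% / 8% |
| +0.5 | worsening 40% / 75% |

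*Sensitivity.* With 50% normalisation at baseline 0, correlation from 0.6 to 0.9 moves the planned test's 58% / 91% over 15-95% / 37->99%. At alpha 0.0033, for a larger Bonferroni family, it is 42% / 82%. The pattern does not change.

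**The case against.** The strongest reply is that normalisation is what the authors mean. The tertiary objective speaks of improved physiological measures of connectivity, and the 3B test asks for greater improvement, whereas the primary test asks for a greater increase in content units. On that reading the defect is one word in the hypothesis plus an unstated sign. This is plausible, and the second repair below serves it. As written, though, the hypothesis and its test still disagree.

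A second reply is that patients may start below the norm. If they do, the planned test points the right way: under 50% normalisation from a baseline of -1 it shows improvement in 97% / >99%, slightly more often than the signed test shows the rise. That stands. But the documents give no baseline coherence and do not restrict the 3B analysis to patients below the norm.

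Two supporting arguments deserve only modest weight. The Background says it is not known whether "normalizing brainwave patterns via EEG neurofeedback training supports and/or enhances increased functional connectivity in the brain", which suggests that one should not be assumed to stand for the other; but that sentence does not discuss coherence z-scores. Hypothesis 2B lists change in coherence without absolute values, but does not say whether it means signed or absolute change.

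It is also fair that the percentages rest on assumed inputs, that the aim is labelled exploratory, that no later trial is said to use coherence as an endpoint, and that signed values could be recovered from the stored data. These points limit the consequence but do not remove the mismatch.

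**Conclusion.** The concern holds. The 3B statistic measures closeness to the norm and the 3B hypothesis asserts an increase. They agree when coherence starts far enough below the norm and does not overshoot it; otherwise the test can reward a fall or miss or penalise a rise. That conclusion needs only the formula and the single-patient examples.

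How often it would matter is unknown, because it depends on baseline coherence. Under the stated assumptions it ranges from near agreement (uniform rise of 0.5 from a baseline of -2: 88% against 92% with a persisting effect) to claimed improvement in 97% of trials when mean coherence has truly fallen by 0.5. The point should be corrected, but it concerns an exploratory aim and leaves the primary analysis untouched.

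**What to change.** Choose one of two wordings for Hypothesis 3B in Sections 2 and 7b.

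1. **If an increase is meant:** make the test statistic the signed change in coherence (follow-up minus baseline, higher meaning greater connectivity), active against sham, in the paired tests already planned. State whether it is on the raw or the z scale. Report the change in absolute z beside it as a descriptive measure of normalisation, with a fall stated as improvement.
2. **If normalisation is meant:** restate 3B as normalisation of coherence, keep the present formula, state that a fall in absolute z is improvement, and draw no conclusion about greater connectivity from it.

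Either is a wording change. The data, bands, paired t-tests and Bonferroni family stay the same, and the descriptive measure adds no test. The signed option has two drawbacks. It counts a rise further above the norm as greater connectivity, which is why absolute z is reported beside it. It will also show nothing if training only normalises around a mean near the norm; a sponsor interested in that effect should take the second option.

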Principal Investigator: [name]
Application Number: IRB00242136
NCT# NCT04290988
Study Title: Circuitry Assessment and Reinforcement Training Effects on Recovery (CARTER)

intervention phase regarding their best-guess as to which type of intervention they are receiving (active versus sham) to assist in determining if they are adequately blinded.

d. Justification of why participants will not receive routine care or will have current therapy stopped.

Participation in this study will not disrupt any current care or therapy. If participants are actively undergoing regular speech therapy while enrolled in this study, we will record the amount of outside speech therapy participants receive during each intervention phase (in terms of number of speech therapy visits and duration of these visits, e.g., 60-minutes) during each intervention phase.

e. Justification for inclusion of a placebo or non-treatment group.

All participants will be participants who will undergo active and sham conditions, thus serving as their own control.

f. Definition of treatment failure or participant removal criteria.

Participants will be removed from the study if they are unable to comply with task instructions or tolerate the EEG neurofeedback, measured by self-report or overt signs of discomfort.

g. Description of what happens to participants receiving therapy when study ends or if a participant's participation in the study ends prematurely.

When the study ends participants will continue to receive management with [name] or their own neurologist as usual (generally follow-up visits every about 6 months). If a patient's participation in the study ends prematurely s/he will still receive care as before. In sum, termination of the study or termination of participation in it will not affect regular treatment he or she may be receiving.

5. Inclusion/Exclusion Criteria

Participants in this study will have a diagnosis of Primary Progressive Aphasia or aphasia following stroke. Diagnostic evaluations will be conducted during the participants' initial visit to confirm aphasia diagnosis.

Inclusion Criteria:

- 1) Diagnosis of PPA or aphasia secondary to stroke and presence of naming deficits with confirmation of diagnosis by neurologist
- 2) Capable of giving informed consent or indicating another to provide informed consent
- 3) Age 18 or older.

Date: November 11, 2021
Principal Investigator: [name]
Application Number: IRB00242136
NCT# NCT04290988

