intention to treat; any missing data will be addressed with the technique of multiple imputation (Rubin, 2004), generally recognized as best for handling missing data (Little et al., 2012).

d. Early stopping rules.

N/A

8. Risks

a. Medical risks, listing all procedures, their major and minor risks and expected frequency.

Two primary instrumental techniques will be utilized, EEG and fNIRS, neither of which have major risks associated. Since EEG neurofeedback is a passive learning process, there is a limit to the extent of negative reactions that can arise as a result of its use (Collura, 2014). Collura discusses two types of abreactions (expression and consequent release of a previously repressed emotion) that might occur as the brain learns self-regulation and normalizes through neurofeedback training. One type of such reactions could be if neurofeedback training results in normalization of a compensatory mechanism that has helped the client cope with particular stresses or other dysregulations. An example could be if a chronically anxious client exhibits excess alpha as a coping mechanism to reduce anxiety. If through neurofeedback training, alpha levels normalize and reduce this coping mechanism, anxiety levels could increase. The long-term goal of neurofeedback is to allow the client to develop healthier circuitry patterns that do not rely on maladaptive patterns in order to cope. The second type of possible abreaction could be the resurfacing of psychological trauma that had been dealt with through coping mechanisms once these coping mechanisms are lessened through more normalized brainwave activity. Another possible negative response is the development of negative effects from current medication regimens as the trainee's brain learns to self-regulate and normalize.

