Participants will be carefully screened prior to being scheduled, to assure that they meet study criteria. EEG neurofeedback sessions will be closely supervised to monitor for any adverse reactions. The participant may stop testing or the intervention at any time. On any given session, if the patient experiences significant frustration, anxiety, or fatigue, that session may be terminated early. Short-term abreaktions will be monitored closely. Those with a history of severe psychological trauma and severe psychological conditions will be excluded from the study.

In the event of a global pandemic (such as COVID-19 outbreak), precautions will be taken to reduce the spread of infection related to the viral outbreak. This includes the following:

1. Remote testing will become the primary mode of testing.
2. If remote testing is not feasible, we will perform home visits whenever possible to limit contact of participants with others at the hospital setting.
3. We also have the option of using the STAR Car, a mobile lab space (wheelchair-accessible van) to reduce the number of people on-campus.
4. If remote testing and/or home visits are not possible, participants may be seen at their outpatient appointment scheduled for clinical follow-up.
 - a. For outpatient appointments, we will limit session room attendance to the participants only (rather than allowing family members to be present in the testing room) and one staff member to administer the session.
 - b. We will also limit lab staff members on-site to essential personnel only, per JHU guidelines.
5. We will screen participants by phone to inquire about recent symptoms and exposure to (e.g., related to COVID-19) before any in-person appointments. Per JHU guidelines, we will defer any appointments (i.e., if any active symptoms are present, we will defer any in-person appointments).
6. Staff will reference JHU policies for self-screening and will defer any in-person or on-campus activities if they suspect that they have any active symptoms (e.g., related to COVID-19).
7. For all in-person visits, we will disinfect test and treatment materials (computers, caps, tablets, pens), devices (EEG amplifier, electrode leads, fNIRS system, optodes) and surfaces (tables, doorknobs) before and after each session.

Date: November 11, 2021
Principal Investigator: [name]
Application Number: IRB00242136
NCT# NCT04290988
Study Title: Circuitry Assessment and Reinforcement Training Effects on Recovery (CARTER)

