8. During in-person visits, staff and participants will wear disposable or cloth face masks, eye shields, and disposable gloves per JHU guidelines.
9. Participants will be asked to use hand hygiene at the beginning of in-person test and treatment sessions before handling equipment; this may include washing hands with soap and water or using hand sanitizing gel/foam approved by the university.

c. Plan for reporting unanticipated problems or study deviations.

Adverse events will be monitored during the entire visit by the study team. The families will be given telephone numbers of study team as well. The study physician ([name]) will be notified immediately if any adverse events are reported. Adverse events will be monitored until they are resolved or clearly determined to be due to a subject's stable or chronic condition or intercurrent illness. Medical care will be provided, as defined in the informed consent, for any adverse event related to trial participation. All adverse events, regardless of intensity or causality, will be recorded in the study documentation and reported to the JHMI IRB. Any serious adverse events will be reported to the JHMI IRB within 24 hours.

Plan for dealing with incidental findings: qEEG will be reviewed by a neurologist if any concerning abnormal findings are present (e.g., possible seizure activity). If an incidental finding is discovered, the site PI ([name]) will call the patient, and arrange to see the patient in clinic on a timely basis to discuss the finding and the plan for medical follow-up (if any). As [name] is the neurologist of the PPA and stroke patients, she will provide care for most of the findings seen on behavioral and physiological assessments, but will refer the patient to other physicians as appropriate.

d. Legal risks such as the risks that would be associated with breach of confidentiality.
Participation in this study should not put participants in any legal risk, even in the case of a breach of confidentiality. We will undertake every effort to keep the information in the study confidential. Participants will be assigned a code number for all data in order to keep the information confidential. The computers on which the information will be stored are password protected. Everybody involved in the study will have completed the appropriate HIPAA training and are fully aware of confidentiality issues. No names will be included in any publications resulting from this work.

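### Adverse events are found by watching during visits and by families telephoning; no one is scheduled to ask about events or medication changes since the last contact, so some between-session events may go unrecorded

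*Combined protocol and SAP*

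**What the plan says.** Section 8c sets out how events are found. During visits, "Adverse events will be monitored during the entire visit by the study team". Outside visits, "The families will be given telephone numbers of study team as well". The study physician "will be notified immediately if any adverse events are reported". Once an event is known, handling is thorough: "All adverse events, regardless of intensity or causality, will be recorded in the study documentation and reported to the JHMI IRB". Serious events go to the IRB within 24 hours, and events are followed until resolved or attributed to a stable or intercurrent condition.

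Section 8b adds that "EEG neurofeedback sessions will be closely supervised to monitor for any adverse reactions" and that "Short-term abreaktions will be monitored closely", without giving a method. Section 4f removes participants who cannot tolerate the training, "measured by self-report or overt signs of discomfort".

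Section 8a names three effects of the training itself: anxiety may rise if a compensatory brainwave pattern is normalized; psychological trauma may resurface as coping mechanisms weaken; and "Another possible negative response is the development of negative effects from current medication regimens" as the brain learns to regulate itself.

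Section 7 specifies paired tests for efficacy and qEEG outcomes. It includes state anxiety (Hypothesis 1E) and frequency of sleep-medication use (Hypothesis 1F), and contains no summary of adverse events.

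**The concern.** The risks in Section 8a are tied to a learning process, not to the minutes spent in the chair. A changed response to a medication taken at home would not necessarily show while the participant trains. For events that show only between sessions, the written route depends on someone volunteering them, and every participant has aphasia. An unprompted account is a weak sole route in that setting, even if participants can signal distress in other ways.

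Two things are at stake. The first is capture of events the protocol itself expects might occur. The second is what the trial passes on. Section 7c describes it as preliminary to a multicenter sham-controlled trial, and a tolerability comparison of active with sham would be a natural product. Without systematic asking, and without counts by condition and period, that comparison is not assured. There is also a smaller analytic cost: an unrecorded medication change in one period could bear on the anxiety, sleep or qEEG outcomes without the analyst knowing.

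**Working it through.** The documents give no adverse event rate, safety sample size or detection probability, so there is no plan figure to reproduce. The main check sets each named risk against the steps that could detect it.

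| Risk (Section 8a) | What the plan has | What is missing |
|---|---|---|
| Raised anxiety | State anxiety at baseline and 1 week after each treatment period, compared between conditions (1E, Section 7b); in-session supervision | No rule that individual worsening counts as an adverse event; no question between assessments |
| Resurfacing trauma | Exclusion of severe psychiatric illness including PTSD (Section 5) and of severe psychological trauma (Section 8b); close watch on short-term reactions | No scheduled measure or question |
| Effects from current medication | General rule that all known events are recorded (Section 8c); frequency of sleep-medication use (1F) | No check on other medications; no general medication record at baseline or later |

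**Contact intervals.** Inputs: 2 to 5 sessions a week (Section 4b), and assessments 1 and 5 weeks after the second period (Section 4a).
- Average spacing during treatment: 7/5 = 1.4 days to 7/2 = 3.5 days.
- Visit 34 to Visit 35: 5 − 1 = about 4 weeks, with no contact described.

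So opportunities to ask are frequent during treatment and absent late in follow-up. The plan does not say the opportunities are used.

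**Illustration under assumptions.** The planned sample is 40 + 40 = 80 (Section 7c), and each participant is to receive active training. Let *p* be an assumed true risk of some event and *s* an assumed share of events captured. Expected recorded events = 80·*p*·*s*. Chance of recording at least one = 1 − (1 − *p*·*s*)^80.

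| Assumed *p* | Assumed *s* | Expected events | Chance of at least one |
|---|---|---|---|
| 5% | 100% | 4.0 | 98.3% |
| 5% | 50% | 2.0 | 86.8% |
| 5% | 25% | 1.0 | 63.4% |
| 2% | 100% | 1.6 | 80.1% |
| 2% | 50% | 0.8 | 55.2% |
| 2% | 25% | 0.4 | 33.0% |

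Neither *p* nor *s* comes from the documents. The table shows only that, in a trial of this size, incomplete capture could hide an uncommon event altogether.

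**The case against.** The strongest reply is that Section 8c does not say staff only watch and never ask. With staff contact every few days, most events would probably be mentioned, and everything mentioned must be recorded. The plan also has real safeguards: the anxiety inventory would show a group-level worsening, the exclusions reduce the trauma risk, and short-term reactions are to be monitored. This stands as mitigation and limits the seriousness of the point. It does not supply a scheduled question, a medication review or a tabulation.

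Three stronger readings are tempting, and the documents do not support them.

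- *Nearly all events are left to volunteered reports.* Visits total 15 × 1.5 h = 22.5 h per period, which is 22.5/504 = 4.5% of 3 weeks or 22.5/1008 = 2.2% of 6 weeks. That is the share of time under observation, not the share of events captured. An event at home can be reported at the next session.
- *The pandemic rules remove the caregiver as reporter.* The restriction in Section 8b keeps families out of the room only at outpatient appointments used when remote testing or home visits are not possible. Families keep the telephone route.
- *Events cannot be assigned to active or sham.* Periods last 3 to 6 weeks and are separated by a week and an assessment, so most events could be placed. Ambiguity is confined mainly to the washout and possible carryover. The fair statement is that no rule requires an onset date.

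Section 8a also gives no latency for these effects, so they should not be called delayed; they arise as training proceeds.

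**Conclusion.** The point holds as a moderate gap in safety data collection that should be closed. Finding events rests on in-visit observation and family telephone calls. No one is scheduled to ask about events or medication changes since the last contact, and no summary by condition is planned. The least protected of the named risks is an effect from a medication other than a sleep aid.

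That events may be under-recorded is an inference about direction. It assumes that scheduled asking finds events which observation and volunteering miss, and that staff do not already ask as unwritten practice. The size cannot be derived. The primary Content Unit analysis does not depend on it.

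**What to change.** At each existing training visit (3–17 and 19–33) and at Visits 18, 34 and 35, ask a short scripted question about adverse events and any medication change since the last contact. Make it accessible in aphasia (yes/no or picture format), with caregiver input in person or by telephone. Participants already answer survey questions on their treatment guess during each phase (Section 4c), so a brief structured item fits the visits.

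- Use identical wording in both conditions.
- State who asks. Section 4c lists participants and the assessing clinician as blinded, but not the technicians who run the sessions. Use blinded staff where feasible.
- At assessment visits, ask after the anxiety inventory so that the question does not influence it.
- Record all current medication at baseline.
- Record onset date and period for each event, and report counts by condition and period.

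The cost is a protocol amendment, a few minutes per visit, and more minor events sent to the IRB under the existing report-all rule. Reporting bias remains possible if unblinded technicians ask. The roughly 4 weeks between Visits 34 and 35 would be covered only by recall at Visit 35.
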